8.4 DATA ANALYSIS

Parasitaemia data will be listed for all enrolled subjects and summarised for the PD population. Parasitaemia and PD parameters will be presented for all subjects included in the PD population.

Parasitaemia profiles

Individual parasitaemia values (parasites/mL), nominal timepoints and actual sampling times post-inoculation will be presented in a data listing. ND and BLQ values will be flagged.

The data will be presented as average of triplicate parasitaemia values for each subject at each timepoint. These data are summarised by calculating the arithmetic mean of the replicate \log_{10} parasitaemia to obtain the geometric mean.

	STATISTICAL ANALYSIS PLAN	QP17C19
		Page 32 of 53

Parasitaemia data will be summarised on the log₁₀ scale by dose group with descriptive statistics at each scheduled timepoint.

The following descriptive statistics will be calculated: N, mean, SD, CV%, median, minimum, and maximum.

Individual parasitaemia data as well as the mean (by dose group) across time will be presented graphically on a log₁₀ scale. Actual sampling times post inoculation will be used for the graphical presentation of data and scheduled timepoints for means.

PD Parameters Determination

PRR₄₈ and parasite clearance half-life (PC_{t1/2})

Processed parasitaemia data (refer to CTM QIMR SOP 87) is used to determine PD parameters.

The data used for all model selection and fitting calculations is comprised of the geometric mean of parasitaemia per timepoint per subject up to the first time all replicates are ND. All subsequent timepoints are set to 'missing', regardless of whether parasitaemia values increased afterwards due to potential recrudescence of malaria infection.

The PD responses will be estimated by calculating the optimal parasite clearance rate (slope coefficient from the log-linear decay regression of qPCR data) for each individual, as detailed in CTM QIMRB SOP 41, and Marquart et al. [7].

A regression modelling method, to incorporate both left and right censoring to remove potential lag and tail phases of the parasitaemia decay curve in a systematic way, will be used to determine the optimal number of data-points required to calculate the slope (β_1) of the log-linear parasitemia decay. A minimum number of 4 timepoints will be required for regression modelling. If fewer than 4 timepoints are used or if the adequacy of the fit to the data is not sufficient (based on the overall model R² p value ≥ 0.001), the slope and derived parameters will be reported as missing.

The individual PRR₄₈ standardised to 48 hours will be derived from the regression modelling versus time in hours as

$$PRR_{48} = 10^{-48 \times \beta_1} \quad (1)$$

The parasite clearance half-life is the transformation of the slope coefficient (per time, equivalent to PRR₄₈) into a time period. The relationship between PRR₄₈ and parasite clearance half-life is a simple transformation of the PRR₄₈, as shown in Equation (2):

$$t_{1/2} = \log_{10}(2) \times \left(\frac{48 \text{ hours}}{\log_{10}(PRR_{48})} \right) = \frac{\log_{10}(2)}{-\beta_1} \quad (2)$$

where the PRR₄₈ is the parasitaemia ratio estimated over a 48 h interval that is subsequently transformed into a per hour clearance rate.

	STATISTICAL ANALYSIS PLAN	QP17C19
		Page 33 of 53

Individual regression plots of parasitaemia over time after treatment will be produced. Data listings of PRR₄₈ and PC_{t1/2} will show the first, last time point and the number of time points used in the regression model.

Weighted mean of regression coefficient (95% CI) of PD endpoints (log₁₀-(Parasitemia) and PC_{t1/2} by dose group) will be plotted by dose group.

Estimating dose group specific PRR (PRR_{48, D})

Of the s subjects with appropriate overall fit ($p < 0.001$), the average PRR₄₈ and corresponding 95% CI for each dose group is estimated by using the inverse variance method [9] to calculate the weighted average linear regression slope ($\bar{\beta}_1$) and corresponding SE. The weighted average slope for s subjects in the dose with appropriate overall fit is given by Equation (3):

$$\bar{\beta}_1 = \frac{\sum_{i=1}^s (w_i \times \beta_{1,i})}{\sum_{i=1}^s w_i}, \quad i = 1, \dots, \quad (3)$$

where the weight is the inverse of the squared SE, $w_i = \frac{1}{SE(\beta_{1,i})^2}$. The SE of $\bar{\beta}_1$ is estimated

$$as, SE(\bar{\beta}_1) = \sqrt{\frac{1}{\sum_{i=1}^s w_i}}.$$

Therefore, the dose group specific PRR (PRR_{48, D}) and corresponding 95% CI is estimated as shown in Equation (4) and (5), respectively:

$$PRR_{48,D} = 10^{-48 \times \bar{\beta}_1} \quad (4)$$

$$95\% \text{ CI: } 10^{-48 \times (\bar{\beta}_1 \pm 1.96 \times SE(\bar{\beta}_1))} \quad (5)$$

Comparison of dose group specific PRR_{48S}

To determine whether there are differences between dose group specific PRR_{48S}, an omnibus test for between dose group differences is used [10]. The test is used to assess whether there are differences in the weighted mean slope of the J doses, using the test statistic shown in Equation (6) at the 5% significance level,

$$Q_B = \sum_{j=1}^J w_j \cdot (\bar{\beta}_j - \bar{\beta}_{..})^2 \sim \chi_{J-1}^2 \quad j = 1, \dots, J \quad (6)$$

The weight for the j^{th} dose is denoted by $w_j = \sum_{i=1}^{s_j} w_{ij}$ for subject i with appropriate overall fit in dose j . The $\bar{\beta}_j$ is the weighted average slope for dose j as defined in Equation (7), and $\bar{\beta}_{..}$ is the weighted grand mean given by:

	STATISTICAL ANALYSIS PLAN	QP17C19
		Page 34 of 53

$$\bar{\beta}_{..} = \frac{\sum_{j=1}^J w_j \bar{\beta}_j}{\sum_{j=1}^J w_j} \quad (7)$$

Interim analyses of comparisons between dose-group specific PRR_{48S} will first be performed for all dose groups within each cohort. Final analyses will include the comparison between the dose groups 1D vs. 3A, each receiving the same dose combination (OZ439 400 mg, PQP 640 mg). Final analyses will be performed based on the factorial design of the study, for the following dose groups to assess differences in increasing PQP dose with constant 200 mg dose of OZ439 (1A vs. 1B vs. 2B), 400 mg dose of OZ439 (1C vs. 1D/3A) and 800 mg dose of OZ439 (2A vs. 3B). Similarly, comparisons will be made to assess differences between dose groups with increasing OZ439 dose with constant 480 mg dose of PQP (1A vs. 1C) and 640 mg dose of PQP (1B vs. 1D/3A vs. 3B). Type 1 error corrections will not be performed as analyses was implicit by the study design.

Post-hoc pair-wise comparisons can be calculated using the test statistic $Z_G = \frac{G}{\sqrt{v_G}}$, where G is the contrast ($G = c_1 \bar{\beta}_1 + \dots + c_j \bar{\beta}_j$) and v_G is the variance of the contrast ($v_G = \frac{c_1^2}{w_1} + \dots + \frac{c_j^2}{w_j}$). The p-value of the L pair-wise comparisons will be calculated using the Scheffe method, by comparing Z_G^2 to a chi-squared distribution with $L - 1$ degrees of freedom.

Recrudescence

Recrudescence will be defined as subjects who show substantial increases in parasitaemia after the initial clearance and are treated with a standard course of Riamet® prior to the compulsory scheduled timepoint for Riamet® treatment.

PD Parameters Analysis

All PD parameters will be listed. Summary statistics will be produced by dose group. For continuous data, the number of observations, mean, SD, median, minimum and maximum values will be reported. The number and percentage of subjects will be reported for incidence data.

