## 10.4 SAMPLE SIZE

A total of up to 24 healthy subjects will be enrolled in the study (to 3 cohorts of 8 subjects each). Subjects will be malaria naïve healthy male or female adults, aged between 18 and 55 years old, who meet all of the inclusion criteria and none of the exclusion criteria.

In each cohort, if more than 2 discontinuations due to safety related reasons occur; additional subjects may be recruited to replace the discontinued subjects on agreement with the study sponsor.

Historically, 8 participants in a dose has proven to be sufficient to characterise the effect of a drug on malaria parasite kinetics following induction of IBSM of healthy subjects.

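### Dose-group PRR48 confidence intervals and between-group tests in SAP 8.4 leave out between-subject variance, so they are too narrow and reject too often whenever subjects differ

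*SAP*

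**What the plan says.** SAP 8.4 fits a log-linear decay to each subject's parasitaemia and takes the slope and its SE.

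- **Group estimate (equation 3).** The average PRR48 "for each dose group is estimated by using the inverse variance method [9] to calculate the weighted average linear regression slope", "where the weight is the inverse of the squared SE". The SE of the group mean is the square root of 1 over the sum of the weights.
- **Interval.** The dose-group PRR48 "and corresponding 95% CI is estimated as shown in Equation (4) and (5), respectively", with a multiplier of 1.96 whatever the number of subjects.
- **Test.** Dose groups are compared "using the test statistic shown in Equation (6) at the 5% significance level", with Q_B referred to chi-square on J-1 df. The pairwise statistic Z_G uses the same weights and also a chi-square reference. Six final comparisons are listed, after interim ones within each cohort, with no type I error correction. One of the six is 1D against 3A, two groups on identical doses.
- **Exclusion.** With fewer than 4 timepoints, or an overall p of 0.001 or more, "the slope and derived parameters will be reported as missing". The group mean is then formed only from the rest: "Of the s subjects with appropriate overall fit". Protocol 10.3.3 also limits the dose-specific PRR to subjects with an appropriate fit.

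SAP 2.1 gives groups of 2 subjects in Cohort 1 and of 4 in Cohorts 2 and 3. SAP 9.4 places inter-individual variability on all PD parameters apart from the Hill coefficient and the interaction terms, with an SD fixed at 0.2 in the SysFit step.

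**The concern.** The SE from one subject's regression measures how precisely that person's slope is known. It does not say how far slopes differ from person to person. Pooling on those SEs alone assumes a single true slope per dose group. Under that assumption, taking more qPCR samples from two people would shrink the dose-group interval towards zero, although nothing more had been learned about other people on that dose. Section 9 of the same SAP makes the opposite assumption.

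PRR48 is a secondary endpoint, and these comparisons are the only ones in the SAP with a stated significance level. If the variance is too small, ordinary differences between individuals are reported as dose effects. The comparison of 1D (2 subjects) with 3A (4 subjects) shows this most clearly: the doses are the same, so a spurious rejection would look like a cohort effect.

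**Working it through.** **Inputs from the documents.** Weights 1/SE², group SE, multiplier 1.96 and the chi-square reference (SAP 8.4); group sizes 2, 2, 2, 2, 4, 4, 4, 4 (SAP 2.1). **Not given:** the between-subject SD of slopes, τ, and the within-subject SE, σ. Results are therefore shown by r = τ/σ.

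**Step 1: formula.** Take σ equal across subjects. A slope then has variance σ² + τ² = σ²(1 + r²), whereas the SAP uses σ². Under equal group means, Q_B is distributed as (1 + r²) times chi-square on J-1 df, whatever the group sizes. Hence:

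- type I error = P(chi-square on J-1 df > c/(1 + r²)), with c the 5% critical value (3.841, 5.991, 7.815 for 1, 2, 3 df);
- CI coverage = 2Φ(1.96/√(1 + r²)) − 1.

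**Step 2: reproduce the nominal figures.** At r = 0 the formulas return 5% for 1, 2 and 3 df, and 95% coverage. The method does what it claims when subjects do not differ.

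**Step 3: let subjects differ.**

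| r | 2 groups | 3 groups | 4 groups | CI coverage |
|---|---|---|---|---|
| 0 | 5% | 5% | 5% | 95% |
| 0.5 | 8% | 9% | 10% | 92% |
| 1 | 17% | 22% | 27% | 83% |
| 2 | 38% | 55% | 67% | 62% |
| 3 | 54% | 74% | 85% | 46% |

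Example at r = 1, two groups: 3.841/2 = 1.921 and P(chi-square on 1 df > 1.921) = 0.166. Coverage at r = 3: 1.96/√10 = 0.620, and 2Φ(0.620) − 1 = 0.465.

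Simulation of the six final comparisons gives a chance of at least one false positive of 23% at r = 0, 64% at r = 1 and 94% at r = 2.

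**Step 4: what r might be.** The p < 0.001 rule limits SE/|slope| to 1/t(0.9995, n−2): 3.2% with 4 points, 11.6% with 6, 16.8% with 8 and 21.8% with 12. If the SD of 0.2 in SAP 9.4 carried over to slopes (an assumption: it is a fixed modelling value for other parameters), r would be at least 0.2/0.218 = 0.9 with 12 points. Two-group error would then be at least about 15%.

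**Step 5: simulated curves.** These used the protocol's inpatient sampling times, with assumed 12-hourly samples to 120 h, residual SD 0.2 to 0.6 log10, half-life 3.6 to 10 h and baseline 10⁴/mL. For 1D against 3A, type I error was 26 to 68% at a slope CV of 20%, and 26 to 47% at 10%. At 0% it was still 8 to 14%, because estimated SEs are treated as known and the fitted points are selected.

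**Step 6: the remedy.** On the equal-SE model, pooling the between-subject variance over 8 groups (24 − 8 = 16 df) with t/F references gave type I error of 4.8 to 5.3% in all six comparisons, and coverage of 94.8 to 95.1%, for r from 0 to 3.

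**The case against.** The best defence is context. PRR48 is secondary, the primary analysis is a PK/PD model with inter-individual variability, and protocol 10.1 says that the study is not powered to compare doses. The inverse-variance method is prespecified and cited. SAP 8.4 also tabulates the SD, minimum and maximum of the PD parameters by dose group and plots each subject's fit, so a reader can see heterogeneity. All of this is true, and it limits the consequences. It does not repair the inference: the tabulated SDs never enter the CI or the test, a citation does not supply the missing variance, and low power does not excuse an inflated false-positive rate. The objection that the size is unknown does stand. At r = 0.5 the two-group error is only 8%.

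Two stronger readings are tempting.

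- **A reader might infer that the p-value rule removes slow clearers and so raises PRR48 most in the low-dose groups.** The documents do not support this. SAP 8.3 extends the fitting data of a subject who never becomes undetectable to 5 days, or to three timepoints after the minimum, so slow clearers tend to have more points. Fast clearers reach undetectable levels after few points and then need an R² of about 0.998 (4 points) or 0.949 (6). In the simulated curves, 0 to 4% of subjects were dropped. They were usually faster than average, and slower only with slow clearance and high noise. Noisier data over a short window could lose more: 35% in one case with residual SD 0.4 over 4 to 72 h. Neither the size nor the direction is fixed.
- **A reader might infer that protocol 10.4 ("Historically, 8 participants in a dose has proven to be sufficient to characterise the effect of a drug on malaria parasite kinetics") also needs restating here.** SAP 2.4 already recasts this as 8 per cohort, for practical reasons, and states that there was no formal power calculation.

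**Conclusion.** The point holds for the variance. Equations 3 to 7 and Z_G are valid only if all subjects in a dose group share one true clearance rate, which conflicts with SAP section 9. Otherwise the 95% intervals are too narrow and the 5% tests reject too often. Over r = 0.5 to 3, type I error is 8 to 54% for two groups and 10 to 85% for four, and coverage is 92 to 46%. These figures assume equal within-subject SEs that are known exactly. The documents do not fix r, so no single figure can be claimed.

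The exclusion rule is a separate and smaller matter. It depends on the outcome and may bias PRR48 in either direction, but it is not the main cause of the narrow intervals.

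**What to change.** 1. In SAP 8.4, replace equations 3 to 7 and Z_G by a linear mixed model, or a one-way model on the subject slopes, with dose group as fixed effect and one between-subject slope variance pooled over the dose groups. Use t and F reference distributions (up to 16 df, fewer if slopes are missing).
2. List the subjects excluded by the p-value rule with their profiles, and add a sensitivity analysis that includes every subject with at least 4 timepoints.

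**Cost.** A revision of SAP text and a few lines of code; the subject slopes are already planned. Intervals on the slope scale widen by a factor of about 1.06 at r = 0, 1.51 at r = 1 and 2.38 at r = 2, and fewer differences will be significant. The model assumes equal between-subject variance across dose groups. Estimating it within each group avoids that assumption but needs t multipliers of 12.71 (2 subjects) or 3.18 (4 subjects), against 2.12 on 16 df.

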## 6.1.5 DOSING AND ADMINISTRATION

### Inoculum

#### P. falciparum 3D7

An inoculum dose, containing an estimated 800 viable P. falciparum 3D7 parasites in infected RBCs in a volume of 2 mL, will be administered intravenously to each subject on Day 0. The actual number of parasites inoculated will take into account the loss of viability resulting from cryopreservation, storage and thawing. On inoculation day, subjects may have food until at least half an hour prior to inoculation. Subjects will undergo intravenous cannulation with an appropriate gauge cannula. Placement patency will be checked by flushing the vein with 5 mL of clinical grade saline. The inoculum will be injected, and the cannula again flushed with 5-10 mL of clinical grade saline. The cannula will then be removed, and haemostasis ensured by use of an appropriate dressing. All subjects will be inoculated intravenously within 60 minutes of each other. See Section 6.1.3 for stability information. An extra syringe will be prepared to quantify the parasite count of the inocula by malaria 18S qPCR.

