### 10.5.1 ENROLLMENT/ RANDOMIZATION/ MASKING PROCEDURES

Randomisation will be performed for subjects in all cohorts. The 8 subjects of all cohorts will be randomised to one of the dose groups each cohort (see Table 1 and 2 Section 4.1) after inoculation day but prior to Day 8.

The randomisation schedule will be generated by a statistician using a validated system. A copy of the randomisation schedule will be sent to the clinical unit pharmacist and clinical unit project manager.

---

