2.1 STUDY DESIGN AND TREATMENTS

This is a single-centre, open-label, adaptive, randomised study using the *P. falciparum* induced blood stage malaria (IBSM) inoculum as a model to characterise the safety, tolerability, PK, pharmacodynamic (PD) activity, and PK/PD relationship of combined single dose administration of OZ439 and PQP.

The study was conducted in three cohorts of 8 subjects each using up to 4 different single doses of OZ439 and PQP in each cohort. Subjects were malaria naïve healthy males or females, aged between 18-55 years old, who met all of the inclusion criteria and none of the exclusion criteria.

The first cohort was composed of 4 groups of 2 subjects each. Subjects were randomised into one of 4 dose groups and administered single oral doses of OZ439 and PQP in combination. The combined dose of OZ439 and PQP was different for each of the 4 groups in this cohort as shown in Table 1.

Table 1. OZ439 and PQP Cohort 1 dose groups

Drug	Dose group			
	1A	1B	1C	1D
OZ439 (mg)	200	200	400	400
PQP (mg)	480	640	480	640

The OZ439 and PQP dose levels and the number of subjects per dose for Cohorts 2 and 3 were determined adaptively during the study.

After review of the PK/PD and safety data from Cohort 1 by the Safety and Data Review Team (SDRT) it was determined that cohort 2 would be composed of 2 dose groups of 4 subjects each. Subjects were randomised into one of 2 dose groups and administered single oral doses of OZ439 and PQP in combination. The combined dose of OZ439 and PQP will be different for each dose group in this cohort as shown in Table 2.

Table 2. OZ439 and PQP Cohort 2 dose groups

Drug	Dose group	
	2A	2B
OZ439 (mg)	800	200
PQP (mg)	960	320

A similar analysis was done at the end of Cohort 2 by combining data from cohorts 1 and 2 to decide the doses to be tested in Cohort 3. Two groups of 4 subjects each were considered. Subjects were randomised into one of 2 dose groups and administered single oral doses of OZ439 and PQP in combination as shown in Table 3.

Table 3. OZ439 and PQP Cohort 3 dose groups

Drug	Dose group	
	3A	3B
OZ439 (mg)	400	800
PQP (mg)	640	640

Each subject was inoculated on Day 0 with approximately 2,800 viable parasites of *P. falciparum*-infected human erythrocytes administered intravenously. Subjects were followed up daily via phone call or text message on Days 1 to 3 post-inoculation to solicit any AEs.

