6.3 DATA HANDLING

Subject Identification Codes

For each cohort, all eligible subjects will be randomised to one of the dose groups on the morning of Day 8.

Randomisation and subject identification codes will be listed. Subject identification codes will be reported in all other listings.

Subjects who are inoculated but do not receive the IP will be included in all safety listing using their subject identification codes.

Assessment Time-Point Identifiers

In the data listings and summary tables presented as part of the CSR, scheduled assessments for Safety data will be identified by the study day name/number and/or protocol scheduled time points (Screening, Day -3 to -1, Day 0, Malaria Monitoring Visit, OZ439 and PQP treatment, and clinical unit confinement, Outpatient Monitoring, Rescue treatment with Riamet® and EOS visit and/or 4, 6, 8, 12, 24 and 72 hours post-OZ439 and PQP dosing), where relevant.

Derived Data

Derived data variables for inclusion in data listings will be calculated as follows:

- Age (in integer years) = (Screening Date – Date of Birth + 1) / 365.25)
- Body Mass Index (BMI) = Weight (kg) / (Height ² (m))
- AE time since Inoculum (in hours, to one decimal place) = (Onset Date + Onset Time) – (Inoculum Date + Inoculum Time).
- AE time since study treatment administration (in hours, to one decimal place) = (Onset Date + Onset Time) – (Study Treatment Administration Date + Study Treatment Administration Time).
- Duration of AE (in hours, to one decimal place) = (Resolution Date + Resolution Time) - (Onset Date + Onset Time).

AE time since Inoculum/study treatment administration and duration of AE will be converted to days (to one decimal place) in the follow-up period.

Handling of Missing Data

Missing values will not be imputed and will be reported in the listings as either “missing” or as the justification for the value being missing e.g. “ND” (not detected), where appropriate.

	STATISTICAL ANALYSIS PLAN	QP17C19
		Page 19 of 53

For the current study the duration of historical medical conditions and prior and concomitant medication administration will not be calculated or summarised and as such missing start and end times/dates will not be imputed.

Descriptive statistics will be calculated from actual data only, with the number of actual data points used for the calculation of the summary statistics reported. Missing data will not be imputed.

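### Four of the five final PRR48 dose comparisons cross cohorts that were not randomised against each other, and 2A vs 3B cannot be separated from cohort

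*SAP*

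**What the plan says.** **Randomisation.** Protocol 10.5.1 has the eight subjects of a cohort "randomised to one of the dose groups each cohort". SAP 6.3 agrees that allocation is by cohort: "For each cohort, all eligible subjects will be randomised to one of the dose groups on the morning of Day 8". (The two documents differ on when randomisation occurs; that does not affect this point.)

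**Choice of doses.** SAP 2.1: "The OZ439 and PQP dose levels and the number of subjects per dose for Cohorts 2 and 3 were determined adaptively during the study". No subject could therefore have been allocated across cohorts.

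**Final PRR48 tests.** SAP 8.4 first plans comparisons of all dose groups within each cohort and calls these interim. It then says: "Final analyses will be performed based on the factorial design of the study, for the following dose groups". The sets that follow are:
- PQP effect at fixed OZ439: 1A vs 1B vs 2B (200 mg), 1C vs 1D/3A (400 mg), 2A vs 3B (800 mg).
- OZ439 effect at fixed PQP: 1A vs 1C (480 mg), 1B vs 1D/3A vs 3B (640 mg).

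A further final comparison sets 1D against 3A, which received the same dose pair. The Q_B test is made at the 5% level without multiplicity correction. Equations 3 to 7 and the pairwise contrast contain subject weights, group mean slopes and a grand mean, but no cohort term.

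**The concern.** A factorial analysis treats every cell as exchangeable apart from dose. Here the cells were filled by three cohorts at three different times. Each cohort had its own inoculation day; Protocol 6.1.5 says "All subjects will be inoculated intravenously within 60 minutes of each other". Anything that shifts clearance rates between cohorts therefore enters a cross-cohort set as if it were a dose effect, and randomisation does not balance it. The results go into Table 14.2.5 and the main text of the CSR, where a difference between Cohort 2 and Cohort 3 could be reported as a PQP effect at the 5% level. This is separate from how the slope variance is computed: it would remain even with a correct between-subject variance.

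**Working it through.** **1. Design (SAP 2.1, Tables 1 to 3), OZ439/PQP in mg.** Cohort 1: 1A 200/480, 1B 200/640, 1C 400/480, 1D 400/640, n=2 each. Cohort 2: 2A 800/960, 2B 200/320, n=4 each. Cohort 3: 3A 400/640, 3B 800/640, n=4 each. Total 4×2 + 2×4 + 2×4 = 24, as the SAP states. The eight groups give 7 distinct dose pairs out of 3×4 = 12 cells. Only Cohort 1 is a complete factorial.

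**2. Final sets by cohort.**

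| Set | Cohorts | Randomised pairs inside the set |
|---|---|---|
| 1A / 1B / 2B | 1, 1, 2 | 1A–1B |
| 1C / (1D, 3A) | 1, 1+3 | 1C–1D |
| 2A / 3B | 2, 3 | none |
| 1A / 1C | 1, 1 | 1A–1C |
| 1B / (1D, 3A) / 3B | 1, 1+3, 3 | 1B–1D, 3A–3B |

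Four of five cross cohorts: one wholly, three partly.

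**3. Can a cohort term separate them?** With the seven dose pairs as categories plus cohort, 2A vs 3B, 1A vs 2B and 1B vs 2B are not estimable, because neither Cohort 2 dose pair recurs in another cohort. The contrasts in the other sets are estimable, because 400/640 mg links Cohorts 1 and 3. Within 1C vs 1D/3A, however, the cohort-adjusted contrast rests on 1C vs 1D alone (2 vs 2).

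**4. Size for 2A vs 3B, assumed range.** The documents give no cohort SD. Let τ be the cohort SD in units of the between-subject SD of the slope, with no dose effect. The group difference has variance 2/4 + 2τ², which is (1 + 4τ²) times the variance that the test assumes. For a two-group F test with 6 df (critical t = 2.447):

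False-positive rate = P(|t₆| > 2.447 / √(1 + 4τ²))
- τ = 0.25: 2.447/1.118 = 2.189, giving 7.1%
- τ = 0.5: 2.447/1.414 = 1.730, giving 13.4%
- τ = 1.0: 2.447/2.236 = 1.094, giving 31.6%

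Simulation on the same basis gives about 6%, 10% and 23% for 1A/1B/2B. At τ = 1.0 it gives about 12% for 1B vs 1D/3A vs 3B and 8% for 1C vs 1D/3A (1D and 3A pooled). For 1A vs 1C the rate stays at 5%. The problem is concentrated in the two sets that use Cohort 2.

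**5. The planned Q_B test.** Assume equal subject SEs, no between-subject variance and one cohort shifted by one per-subject slope SE. For 2A vs 3B the noncentrality is 1²/(1/4 + 1/4) = 2 on 1 df, and the rejection rate is 29%. For 1A/1B/2B with Cohort 2 shifted it is (4×4/8)×1² = 2 on 2 df, and the rate is 23%. With no shift, both are 5%. These are in different units from step 4 and should not be read against it.

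**6. The 1D vs 3A comparison.** With 2 vs 4 subjects and 4 df, the noncentrality for a 1 SD shift is 1/√(1/2 + 1/4) = 1.155, giving 14.7% power. For 2 SD it is 2.309, giving 42.2%.

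**The case against.** **No cohort effect is shown.** This stands. All inocula come from one 3D7 master cell bank with the same target of about 2,800 parasites, treatment is planned for Day 8, and one laboratory supplies the parasitaemia data. The endpoint is a within-subject slope with lag and tail phases removed, so a difference in parasitaemia level alone need not change it. Every rate above 5% in the working is conditional on an assumed shift.

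**The F-test rates are not those of the planned test.** Also true. They isolate the cohort problem from the separate question of Q_B's variance, and must be labelled that way.

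**A reader might infer that randomisation gives no protection in four of the five sets.** The documents do not support that. Only 2A vs 3B has no randomised pair; the other three each keep at least one.

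**A reader might also infer that the SAP fixes the pooling of 1D with 3A.** It writes 1D/3A without saying pooled, although SAP section 5 defines a dose group by its dose combination. Under either reading, Cohort 3 enters both sets.

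**The plan already checks for cohort.** The 1D vs 3A comparison does bear on Cohort 1 against Cohort 3. It is weak, cannot speak to Cohort 2, and has no decision rule attached. The within-cohort contrasts are also prespecified, so the fault is that they are called interim, not that they are absent.

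**The consequence is limited.** PRR48 is a secondary endpoint, and Protocol 10.1 says the study is not powered to compare doses. The primary PK/PD model uses individual growth rate, baseline parasitaemia and PK parameters. This lowers the stakes, but does not make a cohort difference a dose effect in a test at the 5% level.

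**Conclusion.** The point holds as a matter of design. Calling the whole study factorial is wrong, and four of the five final dose sets mix cohorts without adjustment. 2A vs 3B is wholly aliased with cohort, and 2B is aliased with cohort in the 200 mg set. The two sets containing 1D/3A are only partly affected. The size is unknown: the 7%, 13% and 32% for 2A vs 3B rest on assumed cohort SDs of 0.25, 0.5 and 1.0 between-subject SDs, a normal cohort effect and an F test with correct variance. A reader should not conclude that a cohort effect exists, that the dose findings are false, or that the primary PK/PD analysis is undermined; the documents support none of these. The change should be made, but it concerns a secondary analysis.

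**What to change.** In SAP 8.4:
1. Confine the factorial description to Cohort 1.
2. Report the within-cohort randomised contrasts as final rather than interim results: the Cohort 1 2x2 effects, 2A vs 2B, and 3A vs 3B. State that 2A vs 2B changes both drugs together, so it cannot attribute a difference to either.
3. Label 2A vs 3B, 1A vs 2B and 1B vs 2B as non-randomised, descriptive comparisons with no 5% significance claim. With categorical dose, no cohort term can rescue them.
4. For the sets that combine 1D and 3A, stratify by cohort or label them non-randomised.
5. A regression of subject slopes on log dose of each drug plus cohort may be added, but only as a sensitivity analysis. It must state its assumptions (log-linear dose effects, no OZ439–PQP interaction), how slopes are weighted, and how it treats subjects whose slope is set to missing under the SAP 8.4 fit rules.

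The regression should not become the main dose analysis. With all 24 slopes, equally weighted, the cohort term raises the SE of the OZ439 slope from 0.383 to 0.471 and of the PQP slope from 0.647 to 0.704 (between-subject SD units per doubling of dose). Without Cohort 2 the PQP SE is 1.70, so most of the PQP information comes from 2A vs 2B, where both doses rise together. An added interaction term has an SE of about 2.4.

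Cost: SAP wording and, if wanted, one regression; no new data. The cross-cohort sets lose their formal tests, and the remaining randomised contrasts rest on groups of 2 or 4.
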